TITLE: Evaluating the Impact of Community-Driven Grassroots Vaping Interventions on Changing the Attitudes, Perceptions, and Knowledge of Adolescents in Grade 7 and 8 Classrooms

PROTOCOL IDENTIFYING NUMBER: REB23-1437

PROTOCOL VERSION AND DATE: [1; 11, 14, 2023]

GENERAL INFORMATION

SPONSOR: [name], [name] of Medicine, Department of Community Health Sciences, [name], [contact].

STUDY MONITOR: [name], [name] of Medicine, Department of Community Health Sciences, [name], [contact].

INVESTIGATORS:

- [name], [name] of Medicine, Department of Community Health Sciences, [name], [contact].
- [name], Bachelor of Health Sciences Undergraduate Student, Cummings School of Medicine, [contact].
- [name], Bachelor of Health Sciences Undergraduate Student, Cummings School of Medicine, [contact].

Study location: Muriel Clayton Middle School, [name]

STUDY SUMMARY

Title	Evaluating the Impact of Community-Driven Grassroots Vaping
	Interventions on Changing the Attitudes, Perceptions, and
	Knowledge of Adolescents in Grade 7 and 8 Classrooms
Short Title	Vaping Intervention Study
Protocol Identifying	REB23-1437
Number	
Phase	N/A
Methods	Randomized Control Trial
Study Duration	45 - 50 minutes
Study Center(s)	Muriel Clayton Middle School
Objectives	The primary objective of this research is to assess if a video
	produced locally, incorporating extensive stakeholder participation
	and feedback, is more effective than a conventional,
	information-focused video created in a different location.
Number of	Approximately 100
Participants	
Diagnosis and Main	Adolescents in grade 7 or 8 at Muriel Clayton Middle School
Inclusion Criteria	
Study Product, Dose,	Airdrie Board of Youth Affairs Vaping Intervention Video
Route, Regimen	
	5 minutes
Duration of	5 minutes
administration	
Reference therapy	https://www.youtube.com/watch?v=IN7iCZJ3H6w
	What Are the Health Risks of Vaping? - National Institute on
	Drug Abuse (NIDA/NIH)
Analyses	The statistical analysis in the study will focus on using t-tests,
1 mary 505	Mann-Whitney U tests, and linear regression models in Stata 18 to
	assess the effectiveness of an intervention on e-cigarette
	perceptions, adjusting for potential imbalances and exploring
	specific survey items for significant changes.

TABLE OF CONTENTS

STUDY SUMMARY

1.1 Investigational Agent

There is no investigational agent. Instead, we are evaluating the locally produced Airdrie Board of Youth Affairs Vaping Video

1.2 Preclinical Data

This is not applicable.

1.3 Risk/Benefits

There are no potential risks anticipated with the intervention or the assessments. The intervention is non-invasive and the assessments do not ask for sensitive information at all and the only personally identifying information collected is age, gender, and grade. The data will be managed such that the responses are confidential.

The topic of substance abuse may be sensitive to some of the participants. If participants are distressed by the subject matter in the intervention or evaluation their classroom teacher and school counselors will be informed and they can be withdrawn from the study without any negative consequences.

By participating in this trial participants may develop social and emotional competencies, critical thinking and problem-solving abilities, and changed attitudes towards vaping which may help prevent youth vaping abuse. Therefore, this intervention provides an opportunity for participants to better safeguard themselves from vaping abuse and the negative associated consequences. Furthermore, there are also wider potential benefits to study participation. If the intervention works, then it can be widely adopted and thousands could reap the same proven benefits.

1.4 Administration and Dose Rationale

The ABYA video will be administered once to ensure generalizability to real-world implementation of the intervention that will also involve a single viewing.

1.5 Trial Conduct

This study will be conducted in compliance with the protocol approved by the University of Calgary Conjoint Health Research Ethics Board (CHREB), and according to ICH Good Clinical Practice. No deviation from the protocol will be implemented without the prior

review and approval of the CHREB except where it may be necessary to eliminate an immediate hazard to a research participant. In such a case, the deviation will be reported to the CHREB as soon as possible.

1.6 Participant Population

Grade 7 and 8 students from Muriel Clayton Middle School in Airdrie, Alberta, Canada. Students must be able to understand the language of the video and the evaluation questionnaires, any students unable to understand the language due to either language barriers or developmental delays will be identified by the teachers and excluded from the analysis—although they will be provided the option to be present for the room viewings and even fill out the questionnaires to avoid singling them out.

1.7 Literature Review

Vaping refers to the act of inhaling and exhaling aerosol produced by electronic cigarettes (e-cigarettes) or similar devices³. These devices heat a liquid containing nicotine, flavorings, and other chemicals, creating an aerosol that is inhaled by the user^{3,4}. Clinical manifestations of vaping-related lung injury have been observed, and vaping is associated with a range of serious health hazards including nicotine addiction, lung damage, respiratory issues, and cardiovascular problems^{3,4,5}. Furthermore, the presence of harmful chemicals and additives such as acetone, formaldehyde, and heavy metals in e-liquids is of concern, and may also contribute to acute and chronic health issues³.

Vaping can contribute to a range of socio-economic issues. For example, the cost of vaping devices and e-liquids can place a financial burden on individuals and families. Additionally, the marketing and promotion of vaping products can disproportionately target vulnerable populations, such as youth and low-income communities^{7,8,9,10}. Socioeconomic disadvantage has been associated with vaping among never-smoking youth and ex-smoking adults, which suggests a potential to widen health inequalities^{9,10}.

In Canada, approximately 13% of youth aged 15 - 19 and 12% of those aged 20 - 24 have vaped in the past 30 days, compared with only 3% of Canadians over 25^6 . Vaping has thus presented itself as a significant public health concern, especially among youth and adolescents in Canada⁶. The toxicity of electronic cigarettes in adolescents and young adults is of particular concern as the use of e-cigarettes or "vaping" has seen a significant uptick among these demographics⁶. Children and adolescents are particularly vulnerable to the negative effects of vaping due to several factors. E-cigarette companies employ targeted marketing strategies that make vaping products attractive and appealing to young individuals^{11,12,13,14}. The ongoing brain development during adolescence increases susceptibility to nicotine addiction, potentially leading to long-lasting cognitive

consequences and a higher risk of substance use disorders⁷. Additionally, peer pressure Ethics ID: REB23-1437 Date: 1/11/2024 and the desire to fit in or try new trends contribute to the likelihood of children and adolescents engaging in vaping⁸. Furthermore, the easy accessibility of e-cigarettes, both online and in retail settings, allows young individuals to obtain them despite age restrictions⁴.

Misinformation surrounding vaping is a pervasive issue, contributing to its uptake among youth. Misinformation may downplay the risks associated with vaping and be partly responsible for the recent youth vaping epidemic^{15,16,17}. Increasing perceived risk, making these risk perceptions more accurate, and lowering misinformation regarding vaping can reduce youth vaping-associated harm^{17,18}. Therefore, effective public health interventions must be developed for youth to increase perceived risk and lower misinformation. The lack of evidence-based vaping cessation interventions is a concern, and leveraging social media for smoking cessation interventions has been proposed as a viable strategy, given its widespread use among young individuals¹⁸. Interventions observed have primarily been public education and school-based efforts, along with community-based interventions, healthcare provider interventions, aerosol-free policies, age restrictions, and advertising and promotion restrictions¹⁹. This multifaceted challenge requires a concerted effort from public health authorities, educators, parents, and the community at large to mitigate the adverse effects of vaping, particularly among the vulnerable youth demographic.

2 Trial Objectives

- To evaluate the grade 7 and 8 students' attitudes about vaping using the Knowledge and Attitudes regarding e-cigarette ingredients, safety, and addictive properties survey and Harm Perception and Reduction Items survey at baseline (before intervention) and immediately after the intervention.
- To determine student opinions regarding the intervention using the *Video Survey* (appendix) after the viewing.

Other objectives

- To inform on if future substance abuse interventions should involve more or less youth engagement.

3 Trial Design

3.1 Primary Study Endpoints/Secondary Endpoints

The primary endpoints are individual and aggregate item scores on the *Knowledge and attitudes regarding e-cigarette ingredients, safety, and addictive properties survey* (KAS) and *E-cigarette Harm Perception and Reduction Items* (EHI) post-intervention ^{20,21}. The secondary endpoints are the aggregate and item scores on the *Video Survey*.

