7.1 Statistical Methods

Data from questionnaires will be entered into an Excel spreadsheet by research assistants. A double entry will be performed to reduce the frequency of data entry errors. New variables will be created by taking the difference in the individual items and overall scores for KAS and EHI pre and post-intervention for each participant ^{20,21}. In order to ensure that higher scores reflect an increased likelihood of vape abuse, question 10 on the KAS will be reversed scored as a study showed that on this question vape non-users were more likely to score higher than users ²⁰. Descriptive statistics and graphics for participant demographic characteristics and questionnaire responses will be performed prior to primary analysis to detect errors in data, such as missing data and variables being outside of the plausible range. If errors are found they will be addressed. After this, the database will be locked.

Initially, to confirm the validity of creating a total score, we will confirm internal consistency using Crohnbach's alpha. We assume that internal consistency will be adequate and therefore describe an analysis of total scores on the scale in the remainder of this section.

The analysis will begin by describing sample characteristics. Following this, a primary analysis will be undertaken to evaluate the success of the intervention. Imbalances in randomization will be looked at using graphical methods and tables and will be adjusted using linear regressions if the distributional assumptions and the assumption of linearity

are met as assessed with a scatter plot. If the distributional assumptions are not met then quantile regression will be used. T-tests will be performed to assess if the intervention group had a significant change between pre and post-intervention compared to the comparison group on the KAS and EHI. If data is not normally distributed non-parametric tests will be used. The robustness of the primary analysis will be assessed by adjusting for other variables through linear regression models.

An exploratory analysis will be done and will involve using T-tests to determine if the individual item scores for the first 5 questions on the Video Survey are significantly different between the experimental and comparator groups. Mann-Whitney U test will also be used to determine if the two groups responded differently for questions 5 and 6 on the Video Survey.

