An exploratory analysis will be undertaken to specifically explore if the intervention group had a significant change between pre and post intervention compared to the comparison group on the KAS questions 1, 3, and 7 and for the EHI questions 1, 2, 6, 7, 11, and 13. Further analysis looking at all individual items on the KAS, EHI, and video survey will be done to explore if the intervention group had a significant change between pre and post intervention and if the personal information collected impacts scores.

All analyses will be performed on Stata 18.

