7.3 Significance

The alpha value to be used in the study is 0.05.

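### Section 3.1 makes every KAS and EHI item primary alongside the totals, while Section 7.1 treats the items as exploratory; no success rule says which reading governs

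*Protocol*

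**What the plan says.** - **Protocol 3.1** defines the primary family: "The primary endpoints are individual and aggregate item scores on the" KAS and the EHI. Items and totals have equal standing, and only the Video Survey is secondary.
- **Protocol 7.1** announces that "a primary analysis will be undertaken to evaluate the success of the intervention" and makes this an analysis of totals: "We assume that internal consistency will be adequate and therefore describe an analysis of total scores". The test is a between-arm comparison of change: "T-tests will be performed to assess if the intervention group had a significant change between pre and post-intervention compared to the comparison group" on KAS and EHI.
- **Protocol 7.1, later**, gives items a different status. It begins "An exploratory analysis will be undertaken to specifically explore if the intervention group had a significant change" and names the "comparison group on the KAS questions 1, 3, and 7 and for the EHI questions 1, 2, 6, 7, 11, and 13". The remaining items follow as further analysis, also described as exploring.
- **Protocol 7.2** gives 80%-power detectable differences of 1.52 points (KAS) and 3.58 points (EHI) with 50 per arm. It gives none for items.
- **Protocol 7.3** reads in substance: "The alpha value to be used in the study is 0.05". It mentions no split or ordering.

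No section says which primary endpoints, or how many, must be significant for the intervention to be called successful.

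**The concern.** The same item scores cannot be both primary and exploratory. Section 3.1 is where a reader looks to learn what the trial was designed to show, and as worded it would let one significant item be reported as a primary result. Sections 7.1 and 7.2 were plainly written with the totals in mind. Because the protocol does not define success, the choice between the two readings could be made after the results are known.

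The check on internal consistency adds a smaller worry. Section 7.1 uses Cronbach's alpha to confirm that a total score is valid, assumes the answer will be favourable, and gives no threshold or fallback. If alpha were poor, Section 3.1 already gives the items primary status.

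What is at stake is the answer to the trial's main question, whether the local video is more effective than the conventional one. Section 1.3 anticipates wide adoption if the intervention works.

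**Working it through.** **Inputs**
- KAS items: at least 10, because Section 7.1 mentions question 10.
- EHI items: at least 13, because Section 7.1 mentions question 13. The questionnaires are not shown, so both counts are lower bounds.
- Totals: 2.
- Alpha: 0.05 (Section 7.3); two-sided is assumed.
- Sample size: 50 per arm (Section 7.2).
- Correlations between items: not in the protocol, so assumed over a range.

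**1. The plan's own figures.** For two means with n per arm, the detectable difference is (z for 1 − α/2 + z for power) × SD × √(2/n). Here that is (1.960 + 0.842) × SD × √(2/50) = 0.560 × SD. The protocol prints no SD, so I solved for it:
- KAS: 1.52 / 0.560 = 2.71
- EHI: 3.58 / 0.560 = 6.39

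With the t distribution the multiplier is 0.566 and the SDs are 2.69 and 6.33. The stated differences can be neither confirmed nor refuted, but both imply the same standardised effect of about 0.56.

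**2. Section 3.1 read literally, any endpoint sufficient.**
- Number of tests: 10 + 13 + 2 = 25
- Expected false positives under the null: 25 × 0.05 = 1.25
- Chance of at least one, if independent: 1 − 0.95^25 = 0.72

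The totals are sums of the items, so independence cannot hold exactly. A simulation with 8,000 trials per setting, 50 per arm and the totals built from the items gave:

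| Item correlation within scale / between scales | At least one of 25 | At least one of 2 totals |
|---|---|---|
| 0 / 0 | 70% | 9.6% |
| 0.3 / 0.15 | 62% | 8.8% |
| 0.5 / 0.25 | 51% | 9.3% |
| 0.5 / 0.5 | 46% | 6.4% |
| 0.7 / 0.5 | 35% | 8.4% |

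A simpler model with all 25 tests equally correlated gives 66% at 0.2, 47% at 0.5 and just over 30% at 0.7.

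**3. Section 7.1 read literally, either total sufficient.** 1 − 0.95² = 0.0975. Correlation between the totals lowers this; at 0.7 it is about 8.3%.

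**4. All primary endpoints required.** There is no inflation, but power falls.

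**5. Two totals, each at 0.025.** The multiplier is (2.241 + 0.842) × √(2/50) = 0.617.
- KAS: 2.71 × 0.617 = 1.67 (t-based 1.68)
- EHI: 6.39 × 0.617 = 3.94 (t-based 3.95)
- Power at the stated 1.52 and 3.58: Φ(2.802 − 2.241) = Φ(0.56), about 71%
- Sample size to restore 80%: 50 × (0.617 / 0.560)², about 61 per arm

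**6. All 25 endpoints kept primary with Bonferroni.** Each is tested at 0.05 / 25 = 0.002, and power at the stated differences is about 39%.

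**The case against.** The strongest reply is that a reader might infer from Section 3.1 that the trial's false-positive rate is simply far above 5%, and the documents do not support that. No section says one significant item is enough. The only text tying an analysis to success is in Section 7.1, which plans on totals, and Section 7.2 gives figures for the scales only. On that reading there are two tests and an error of at most 9.75%. This stands: the larger figures are conditional on an any-endpoint rule that the protocol does not contain. They also rest on lower-bound item counts and assumed correlations.

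It is also fair to say that a multiplicity method, or a success rule across two scales, may sit in an analysis plan that is not shown. Their absence alone is no fault here. The endpoint conflict is different, because it lies within the protocol and a later plan would inherit it.

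Finally, a reader might infer that the protocol switches the primary family to items if Cronbach's alpha is low. It does not say so, and nothing suggests alpha would be computed by arm. What remains is a risk, arising because the check has no fallback and Section 3.1 already gives the items primary status.

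**Conclusion.** The contradiction over the status of the items is firm and needs no assumption: Section 3.1 cannot be reconciled with Section 7.1 as written, and Section 7.2 fits only the latter. It should be resolved before the data are analysed.

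Its effect on the error rate depends on the success rule applied. With Section 3.1 and any endpoint sufficient, it is 72% under independence and about 30% to 70% across the assumed correlations. With Section 7.1 and either total sufficient, it is at most 9.75%. The promotion of items after the Cronbach's alpha check is an inferred risk, not a stated rule.

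**What to change.** - **Section 3.1:** name the KAS total and the EHI total as the only primary endpoints, tested with Holm at an overall two-sided 0.05. Alternatively, name one total as the single primary endpoint.
- **Items:** make all item-level results exploratory, in line with Section 7.1, and report them as estimates with confidence intervals.
- **Cronbach's alpha:** compute it on pooled baseline data, blind to arm, and state that the result cannot move primary status to the items.
- **Sections 7.1 and 7.3:** align them with the new definition and the alpha actually used.
- **Section 7.2:** restate the detectable differences at that alpha.

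The cost is wording plus some power. With two totals, the 80%-power detectable differences at alpha 0.025 become about 1.67 to 1.68 (KAS) and 3.94 to 3.95 (EHI), and power at the stated differences is about 71%. Holm softens this, since once one total is significant at 0.025 the other is tested at 0.05. The sample is limited to the school's grade 7 and 8 students, so recruiting to about 61 per arm is probably not open. A single primary total leaves alpha and that scale's detectable difference unchanged, at the price of demoting the other scale.

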5.2 Method and Timing

The two adapted versions of the validated surveys assess attitudes and perceptions in relation to e-cigarette or "vaping" use. The students will be informed by their teachers prior to survey distribution that e-cigarette terminology and vaping are interchangeable. For both of the surveys, participants rate how much they agree with each statement (on a numbered scale between "*strongly disagree*" and "*strongly agree*") related to vaping/e-cigarette use (*e.g. "e-cigarettes are safer than smoking"*). To determine if there was any difference in attitudes, knowledge, or harm perceptions related to vaping before and after the intervention.

Demographic information collected in the personal information questionnaire will include age, gender, and grade. This information will be used to describe the sample recruited and assessed for variations between different groups. No other identifying personal information will be collected (name, contact information, etc.) and all results will be anonymous.

The *Video Survey* is a questionnaire adapted from a previous study (Hollis et al., 2022) asking students regarding their opinion of the intervention's effect on their vaping knowledge, usefulness to others, and overall knowledge about vaping following the intervention ². This information will be collected to determine how the intervention was perceived by the participants. Students will also be asked if they have vaped to inform on the effect of prior vape use on the perception of the intervention and efficacy and changing attitudes. Short answer questions asking participants what they liked and what they disliked in the intervention will also be included to inform future directions.

6 Assessment of Safety

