7.2 Sample Population(s) for Analysis

Our sample size is limited to the number of grade 7 and 8 students at Muriel Clayton school, approximately 100 students with 50 in the control group and 50 in the experimental group. Based on existing literature on standard deviation (SD) of the surveys we determined the effect size our study can detect with 80% power ^{20, 21}. We determined that our study can detect a difference of 1.52 points on the KAS scale and a 3.58 points on the EHI with 80% power. A study showed that for the KAS cigarette/e-cigarette users and non-users had a mean score of 21.04 and 18.86 respectively when reverse scoring question 10 ²⁰. Considering the difference between the two groups in this study is similar, we have the statistical power to detect it.

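### The endpoint, analysis and power sections do not describe one primary variable: Section 3.1 names post-intervention scores, Section 7.1 tests pre-to-post change, and Section 7.2 works from score-level figures

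*Protocol*

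**What the plan says.** Protocol Section 3.1 defines the primary endpoints as individual and aggregate scores on the knowledge and attitudes survey (KAS) and the harm perception items (EHI): "KAS) and *E-cigarette Harm Perception and Reduction Items* (EHI) post-intervention". It mentions neither baseline nor change. Section 3.2 uses the same term for the questionnaires numbered 2, which students complete after the video.

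Section 7.1 works with a different quantity: "New variables will be created by taking the difference in the individual items and overall scores for KAS and EHI pre and post-intervention". Its primary test follows: "T-tests will be performed to assess if the intervention group had a significant change between pre and post-intervention compared to the comparison group". Non-parametric tests replace the t-test if the data are not normal. Regression appears for imbalances in randomization and as a robustness check with other variables; the baseline score is not named as a covariate. No between-group test of the post-intervention KAS or EHI score is described anywhere.

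Section 5.2 leans the same way as Section 7.1: "To determine if there was any difference in attitudes, knowledge, or harm perceptions related to vaping before and after the intervention". Section 2 says that attitudes are measured "at baseline (before intervention) and immediately after the intervention", which fits either variable.

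Section 7.2 assumes "approximately 100 students with 50 in the control group and 50 in the experimental group" and gives detectable differences of 1.52 points (KAS) and 3.58 points (EHI) at 80% power. It derives them from a literature SD of the surveys, whose value is not stated, and compares the KAS figure with mean scores of 21.04 in users and 18.86 in non-users. It gives no SD of change and no pre-post correlation.

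**The concern.** A post-intervention score and a change score have different variances and respond differently to chance baseline imbalance. If the endpoint section names one and the analysis section tests the other, a report of post scores could cite Section 3.1 and a report of changes could cite Section 7.1, each claiming to be pre-specified. A reader could not then tell whether the primary endpoint had been switched.

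The power statement is also affected. Its inputs look like score-level figures, so it is closer to Section 3.1 than to the test in Section 7.1. Whether 1.52 and 3.58 points apply to the planned test depends on a correlation that the protocol does not give.

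**Working it through.** **Inputs from the protocol.** 50 per arm and 80% power (Section 7.2); detectable differences 1.52 (KAS) and 3.58 (EHI) (Section 7.2); alpha 0.05 (Section 7.3: "The alpha value to be used in the study is 0.05").

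**Assumptions.** Two-sided testing (not stated); equal pre and post SDs; the unstated SD in Section 7.2 is that of a score level; pre-post correlation r from 0.3 to 0.8.

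**The plan's own figures.** They cannot be reproduced independently because the SD is not given. Solving backwards with the normal approximation, SD = difference / [(1.960 + 0.842) × √(2/50)] = difference / 0.560. This gives about 2.71 for the KAS (1.52/0.560) and 6.39 for the EHI (3.58/0.560). A one-sided test would imply 3.06 and 7.20.

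**Variance of change.** SD of change = SD × √(2(1 − r)). The detectable difference for a change-score test is therefore the stated figure × √(2(1 − r)). For the KAS at r = 0.3: 1.52 × √1.4 = 1.80.

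**Correlation between the two variables.** Cov(post, change) = SD²(1 − r) and Var(change) = 2·SD²(1 − r), so the correlation is √((1 − r)/2): 0.59, 0.50, 0.39 and 0.32 at r = 0.3, 0.5, 0.7 and 0.8.

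**Disagreement.** Two test statistics with that correlation were simulated (bivariate normal, 2 million draws). With no effect, the quantity of interest is the chance that at least one is significant. At the stated difference the post-score test has noncentrality 2.8 and the change test 2.8/√(2(1 − r)); here it is the chance that exactly one is significant.

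| r | KAS detectable, change | EHI detectable, change | Power of change test at 1.52 / 3.58 | Exactly one significant, true difference 1.52 | At least one significant, no effect |
|---|---|---|---|---|---|
| 0.3 | 1.80 | 4.24 | 66% | 26.7% | 8.8% |
| 0.5 | 1.52 | 3.58 | 80% | 22.6% | 9.1% |
| 0.7 | 1.18 | 2.77 | 95% | 20.2% | 9.4% |
| 0.8 | 0.96 | 2.26 | 99% | 20.0% | 9.5% |

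A separate simulation of 40,000 trials per scenario, with t-tests on 50 per arm and KAS SD 2.71, agrees. Verdicts differ in 27%, 23% and 21% of trials at r = 0.3, 0.5 and 0.7, and at least one test is significant under no effect in 8.6%, 8.7% and 9.2%.

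**Baseline-adjusted post score, for comparison.** The residual SD is SD × √(1 − r²), so the KAS detectable difference is 1.52 × √(1 − r²) = 1.45, 1.32 and 1.09 at r = 0.3, 0.5 and 0.7.

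**The case against.** The strongest reply is that the post-intervention wording in Section 3.1 is only a time label, and that Section 7.1 supplies the metric. The study is described as a pre/post design, Section 5.2 speaks of a before-and-after difference, and the only between-group KAS and EHI test in the primary analysis is on change. A report resting on post scores alone would depart from the written analysis. Much of this stands: change is the likelier intention. It does not remove the mismatch. Section 3.1 names the score and not the change, and the power inputs in Section 7.2 are in score-level terms.

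Three stronger readings are tempting, and the protocol does not support them:

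- **The trial runs at about 9% false positives.** That requires an analyst to be free to choose between two tests. Section 7.1 describes one.
- **The two variables can give opposite answers about direction.** Under randomization they share the same expected between-group effect. In the t-test simulation (r = 0.3 to 0.9), both tests were significant in opposite directions in at most 0.04% of trials, and at a true difference of 1.52 the estimates differed in sign in under 1%. The disagreement is between significant and not significant.
- **1.52 and 3.58 points can simply be relabelled as changes.** If the SD is a score-level one, this is right only at r near 0.5.

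**Conclusion.** The point holds as an inconsistency among Sections 3.1, 7.1 and 7.2 over what the primary variable is. It is not evidence that the planned test is invalid or that an endpoint has been switched.

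Its practical size has two parts. First, the choice of variable alters the significance verdict in about one trial in four to five at the design difference. Second, power for the Section 7.1 test at the stated differences could be anywhere from 66% (r = 0.3) to 95% (r = 0.7), where Section 7.2 states 80%. Both rest on the assumptions listed, above all the score-level SD and the range of r, since the protocol gives neither the SD nor the correlation. The matter is worth settling before data collection, and it is not fatal to the trial.

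**What to change.** Name one primary variable in the same words in Sections 3.1 and 7.1. Either of two would resolve the conflict: the between-group difference in pre-to-post change that Section 7.1 already tests, or the post-intervention total adjusted for its own baseline score, which stays closer to Section 3.1. State that any unadjusted comparison of post-intervention scores is descriptive.

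Then restate the detectable differences in Section 7.2 for the chosen variable, showing the assumed SD, what it is an SD of, and the assumed pre-post correlation with a range. Do not carry 1.52 and 3.58 points over unchanged under a new label.

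The cost is a few sentences of wording and one recalculation, with no new data. The possible downside is a less favourable detectable difference, for example 1.80 instead of 1.52 KAS points if change is chosen and r is 0.3.
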